Coordinating investigator	PD [name], Klinik für Neurochirurgie, Universitätsklinikum Münster, [name]
Investigators	[name]
Title	Multi-center-registry trial on surgical outcome and quality of life in juxta-medullary tumors
Indication	Adult patients operated on juxta-medullary tumors
Study objectives	
Primary objectives:
 
Primary objectives are to assess and define benchmarks of the surgical outcome in the form of extent of resection, functionality, and quality of life after resection of juxta medullary tumors
 
Secondary objectives:
 
Assessment of variables leading to better outcome through regression analysis:
 
1. Influence of surgical approach on functionality, pain, and quality of life2. Comparison between patient with severe neurological (McCormick scale 3-5) to patients with mild deficits (McCormick 1-2)3. Role of IOM in extent of resection and neurological deficits 
Assessment of treatment variations:
 
1. Assessment of risk factors for incomplete resection2. Non inferiority of unilateral approach to achieve gross total resection of spinal meningioma, schwannoma and cauda ependymoma3. Role of bed rest after surgery to prevent cerebro-spinal fluid leakage4. Influence of laminectomy on cerebro-spinal fluid leakage 
Quality indicators: assessments of length of hospital stay, 30- and 90-days readmissions, 30- and 90-days re-surgery, nosocomial infections

Inclusion/Exclusion criteria	
Inclusion criteria
 
• Adult, age ≥ 18 years, patients treated on intraspinal, extra medullary tumor• Patients must have sufficient cognitive and language skills to give informed consent

	
Exclusion criteria
 
 • Absence of informed consent • Lack of ability to consent • Primary bone tumors invading the intra-spinal space • Vertebral metastasis

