2.2 Rationale of the study

The rationale of the trial is to define benchmarks on quality of life, functionality and neurological outcome after resection of juxtamedullary tumors. Furthermore, to assess and define benchmarks of quality indicators of the treatment. These measurements would be essential for future studies.

Further rationales are to find out the optimal timing, method, and approach to treat juxta-medullary tumors. Because of the low incidence of juxta-medullary tumors, a multi-center trial seems to be essential. This would allow us to analyze a large number of patients, much more than any other published paper. Moreover, the different protocols and standards approaches in each center would allow conducting Comparative Effectiveness Research (CER).

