2.3 Aims

The goal of this study is to establish a multicenter cohort of patients operated on juxtamedullary tumors. With especial emphasis on functional outcome, quality indicators (QI) and quality of life after surgery three months after surgery. Causes of unfavorable outcome should be determined (Schipmann et al., 2017, 2019).

The main hypothesis is that early and less-invasive surgery with maximal extents of resection would lead to a more favorable outcome. In the future the registry would help assessing further hypothesis can be answered on the base of comparative effectiveness research (CER), examples of these hypothesis are:

1. Functional and neurological outcome in comparison to preoperative status. Comparison between Patients with good preoperative McCormick score (1-2) and those with a high preoperative score (3-5).
2. Risk-factors for non-favorable outcome
3. Non-Inferiority to achieve gross total resection via unilateral approaches
4. Question whether laminectomy as approach may cause more pain and impact quality of life
5. Risk factors for the development of CSF Leaks
6. Does bed rest prevent CSF leaks
7. Does laminectomy elevate the risk of CSF leaks
8. Does the utility of intraoperative neurophysiological monitoring (IOM) influence surgical outcome: rate of GTR and neurological outcome
9. Rate of postoperative kyphosis and deformity in laminectomy in comparison to non-laminectomy

10. Is facetectomy required for GTR of dumbbell tumors?

11. Risk factors for non-complete resection

Primary outcomes are determined by:

- Quality of life based on the questionnaire (EQ-D5)
- Extent of tumor resection (see CRF):
according to surgeon:
 1. Meningioma: Simpson grade 1 and 2
 2. Schwannoma: complete resection, including nerve root
 3. Cauda ependymoma: complete resection, including filum terminale
according to postoperative MRI, 3 months after surgery
 4. Other: surgeon's decision
- Neurological status (McCormick Score) (see CRF), 3 months after surgery

Secondary Outcome

Imaging: preoperative and postoperative MRI

- Volumetry
- Spinal canal occupancy ratio in %

Further patient reported outcomes:

- Functionality: Neck disability index (NDI) for tumors in the cervical spine, Oswestry disability index (ODI) for tumors in the thoracic and lumbar spine (see CRF)
- Local and radicular pain (VAS 1-10) (see CFR)
- Neurological status: motor function of each limb, ataxia and gait (mJOA score) (see CRF)
- HADS score- based score for anxiety

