- Questionnaire on bladder, bowel, sexual functionality

Quality indicators (QI):

Length of hospital stay

30- and 90-days readmission

Nosocomial infections

Blood loss

Duration of surgery

Progression of the disease or recurrence

Other adverse events

Mortality

Assessment of adverse events according to Common Terminology Criteria for Adverses Events (CTCAE) 5.0 and severity according to the Ibañez scale (see CRF)

CSF leakage is defined as one, when CSF leakage is identified on imaging of clinicaly and treatment is required: operative or conservative (Lumbar drain for example)

Postoperative kyphosis or deformity is defined, when symptomatic (for example pain) or evident on imaging (for example kyphotic fracture on MRI)

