2.4 Risk-Benefit Analysis

2.4.1 Risk expected for participants

No risk whatsoever awaits the participants in the study. All examinations and interventions will be performed according to clinical routine. Refusal to participate in the study will not result in any disadvantages for the patients. Participants will be treated exactly like non-study participants, based on the therapy standards of the respective study center

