3.2.3 Distribution of Gender in the Study Population

All patients treated on juxta-medullary tumors can be invited to participate in the study; distribution of Gender varies depending on histology. For example, spinal meningiomas are up to 80% in female patients (Schwake et al., 2018).

4. Patient Registration

Patients who are cared for at one of the study sites and who are possibly eligible will be invited for study participation. Once written informed consent in participation has been given, the center can register the patient in the electronic data base (Redcap).

Should inclusion criteria fail, or exclusion criteria arise during the following screening process, the patient must be reported to the study coordinator immediately and the patient will be withdrawn from the study.

5. Assessment of Safety

Patients are treated according to the protocol of each center, the participation in the trial does not cause any disadvantage for these patients. Both patients' safety and possible adverse events are

subjects of this study.

6. Statistics

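### A CSF leak counts only if treatment is required, so for the bed-rest question the outcome can depend on, and overlap with, the exposure

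*Protocol*

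**What the plan says.** The definition appears in the Synopsis (outcomes) and again in section 2.3 Aims (quality indicators): "CSF leakage is defined as one, when CSF leakage is identified on imaging of clinicaly and treatment is required". The treatment condition, "treatment is required: operative or conservative (Lumbar drain for example"), allows operative or conservative treatment, with a lumbar drain as the only example. It gives no closed list of conservative measures and no common threshold for when a leak requires treatment.

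Two exposures are to be studied against this outcome:

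- **Bed rest.** The Synopsis lists "Role of bed rest after surgery to prevent cerebro-spinal fluid leakage" among the treatment variations, and section 2.3 Aims asks "Does bed rest prevent CSF leaks".
- **Laminectomy.** Section 2.3 Aims asks "Does laminectomy elevate the risk of CSF leaks", and the Synopsis has a matching item.

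Management is local. Section 2.4.1 says that participants are treated "based on the therapy standards of the respective study center", and section 5 (Assessment of Safety) says "Patients are treated according to the protocol of each center". Section 2.2 makes this variation the basis for comparison: "the different protocols and standards approaches in each center would allow conducting Comparative Effectiveness Research (CER".

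**The concern.** The study questions are about whether leaks occur. The definition counts leaks that are judged to require treatment. These differ whenever a leak is seen and left untreated, and the decision to treat belongs to the centre.

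For bed rest this matters in two ways.

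- **Outcome depends on exposure.** Where bed rest is routine, a small leak may settle without anything being recorded as treatment, and so may not count. Where it is not routine, bed rest ordered for the same leak could be taken as the conservative treatment that makes it count.
- **Exposure depends on outcome.** Nothing in the protocol separates bed rest given to prevent a leak from bed rest given because of one. If the second kind is coded as exposure, patients with leaks are moved into the bed-rest group.

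The first mechanism can make bed rest look protective, and the second can make it look harmful. A comparison built this way cannot be interpreted without knowing how each centre treated and recorded its leaks. The registry also aims to set benchmarks for later studies, and a CSF-leak benchmark under this rule is a treated-leak rate tied to local thresholds.

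**Working it through.** The protocol gives no figure that rests on this definition, so there is none to reproduce. The check is a reading of the definition followed by an illustration of scale.

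**1. What the definition includes.** I read the misprint in its detection clause as imaging or clinically. An event then needs detection and required treatment. An identified but untreated leak is not an event. Conservative treatment is open-ended, and bed rest is non-operative and not excluded.

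**2. Inputs.**
- Leak rate: about 1-4%, with 4.27% in a cited series of 398 patients (section 2.4.5). Using this as the rate of all leaks is an assumption, because the section does not say whether untreated leaks are included.
- Sample size: 100 (Synopsis; section 2.3 Methodology).
- Share of leaks counted under each policy: not in the protocol; assumed.
- Split between bed rest and no bed rest: not in the protocol; 50 against 50 assumed.

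**3. Effect of uncounted leaks.** Counted rate = leak rate × share counted. With the same leak rate in both groups, the apparent risk ratio is the ratio of the shares, and the true ratio is 1.0.

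| Share counted, policy A | Share counted, policy B | Counted rates at 4% | Apparent risk ratio (B/A) |
|---|---|---|---|
| 100% | 75% | 4.0% vs 3.0% | 0.75 |
| 100% | 50% | 4.0% vs 2.0% | 0.50 |
| 90% | 70% | 3.6% vs 2.8% | 0.78 |
| 90% | 50% | 3.6% vs 2.0% | 0.56 |

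The ratio does not depend on the leak rate. At 1%, the first two rows give 1.0% against 0.75% and 0.5%, with the same ratios. If the undercounting lies in the other group, the first two ratios invert to 1/0.75 = 1.33 and 1/0.50 = 2.00.

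**4. Number of events.** 100 × 0.01 = 1 and 100 × 0.04 = 4 leaks (4.27 at the cited series' rate). At 4% with 50 per group and no true effect, each group has 2 leaks. Leaving one uncounted gives 1/50 against 2/50, a ratio of 0.50.

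**5. Effect of recoding exposure.** Start from the same 2/50 and 2/50. If one leak in the group without bed rest leads to bed rest and is coded as exposed, the groups become 3/51 and 1/49. The ratio is 0.0588 / 0.0204 = 2.9. One patient moves the result in the opposite direction to step 4.

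**6. Laminectomy.** If the same share s of leaks is counted in both approach groups, the ratio is (p1 × s) / (p0 × s) = p1/p0, which is unchanged. Distortion of the ratio needs s to differ by approach, for example because centres that prefer laminectomy also have a different threshold for treating leaks.

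**The case against.** The case on the other side has real content.

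- **Bed rest is never named as a qualifying treatment.** The one example, a lumbar drain, points to active intervention. A reader might infer that the protocol counts bed rest as treatment, so that outcome and exposure overlap by definition. The text does not say so. It only fails to exclude bed rest, which makes overlap possible.
- **Required need not mean newly ordered.** A leak managed by continuing existing bed rest could still be one for which treatment is required. Undercounting in routine bed-rest centres is therefore one permitted reading among others.
- **The CRF is not shown.** It may record untreated leaks, treatment given or the timing of bed rest. The Ibañez scale in section 11.9 already separates complications managed without invasive procedures from those needing them. This would ease the repair, but the definition would still exclude untreated leaks from the event count.
- **Events are scarce in any case.** With 50 per group, a true halving from 4% to 2% has about 8% power at a two-sided 5% level, and 80% power needs about 1,141 per group. That is a separate limit. It does not make a policy-dependent outcome acceptable, least of all for a benchmark.
- **An any-leak outcome has its own dependence.** The flow chart in section 1.2 schedules postoperative MRI only at 3 and 12 months, so earlier detection on imaging follows local practice. Counting only treated leaks is a defensible choice of clinically relevant events. This stands, and is the reason to report both rates.
- **The question is secondary.** CSF leakage is not a primary outcome, and section 2.3 Aims presents the bed-rest question as an example for future work, although the Synopsis lists it under secondary objectives.

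A reader might also infer that the laminectomy comparison is biased in the same way. Step 6 of the working shows that this needs a link between approach and treatment threshold, which the documents do not establish.

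**Conclusion.** The concern holds in a limited form. As written, the definition allows the local policy that supplies the bed-rest contrast also to influence which leaks count. It leaves room for bed rest to be both the exposure and the qualifying treatment. The CSF-leak benchmark is a treated-leak rate that depends on centre threshold. That is a different quantity from leak occurrence, and not by itself a biased one. The laminectomy comparison is affected only if approach and threshold are linked, for instance through centre.

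The illustrated size, a spurious risk ratio of 0.75 to 0.50 at a 4% leak rate, rests entirely on the assumed share of a quarter to a half uncounted under one policy. A reader might infer from it that the rule favours bed rest. The documents do not support that, because the direction is undetermined. The firmer statement is that with about 1 to 4 leaks in 100 patients, one or two reclassified leaks change the result. The outcome is secondary, but the definition should be changed because the change is cheap and leaks never recorded are hard to recover later.

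**What to change.** - Record every CSF leak identified on imaging or clinically, and correct the misprint in the detection clause.
- Record as separate items how the leak was detected and what treatment was given (none, conservative, drain, operative).
- For the bed-rest analysis, define exposure as the bed-rest order set at the end of surgery, before any leak. Bed rest by itself should not make a leak count as an event.
- Report both the any-leak and the treated-leak rate.

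The cost is a change of wording and one or two CRF items, fewer if the CRF already holds them. The stated leak rate will be somewhat higher. The any-leak rate will still depend on local imaging practice, so the treated-leak rate stays alongside it, also for comparison with the literature. These are changes to recording and analysis only; no change to patient management is proposed.

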2.3 Methodology

All patients treated in one of the study centers are recorded in a databank (Redcap, see below), which includes information about admission, symptoms, other diseases, treatment, quality indicators and questionnaires regarding quality of life and functionality. Data should be recorded in an anonymized in each center (see below).

For the analysis the CRF includes information about admission, surgery, discharge, and 3 months (90 days) after surgery. In addition, patients should fill out questionnaires on quality of life (EQ-D5) and functionality (ODI or NDI). Later, yearly visits can be completed to have long term results in the future regarding progression free survival (PFS) and overall survival (OS). The CRF is attached to this document.

Univariate and multivariate statistics would be applied to prove which variables might lead to a favorable or unfavorable outcome.

A minimum number of one hundred (N=100) inclusions seems to be adequate in order to perform reasonable analysis. In the event of nonsufficient recruitment, results and further recruitment would be discussed two years after initiation of the study, and annually thereafter.

2.4 Risk-Benefit Analysis

2.4.1 Risk expected for participants

No risk whatsoever awaits the participants in the study. All examinations and interventions will be performed according to clinical routine. Refusal to participate in the study will not result in any disadvantages for the patients. Participants will be treated exactly like non-study participants, based on the therapy standards of the respective study center

2.4.2 Benefit expected for participants

There is no specific benefit for the participants by taking part in the study

2.4.3 Benefit expected for medical science

The study should determine factors that influence the outcome (degree of resection, neurology, quality of life functionality, pain) of the patients. Furthermore, it would determine factors that influence the quality of treatment (length of stay, 30-day readmission, complications, infections etc.).

2.4.4 Benefit expected for the society:

A postoperatively impaired quality of life, severe neurological deficit, or functionality often leads to high costs in the health and social care systems. Therefore, knowledge of influencing factors is also of imminent societal importance.

In addition, quality indicators of therapy should be determined. These are also important for society. Improving the quality of therapy, for example, by reducing the length of stay, postoperative complications can also reduce treatment costs.

2.4.5. List of possible adverse events

Cerebrospinal Fluid (CSF) Leak:

- **Incidence:** Approximately (aprox. 1-4 %)

Details: A study involving 398 patients reported a CSF leak-related complication rate of 4.27%. The use of 6-0 Prolene sutures for dural closure was associated with a lower leak rate compared to 5-0 silk sutures.

Neurological Deficits:

- **Incidence:** Weakness (aprox. 5-20%), new sensory deficits (aprox. 4-16.7%)

Details: In a cohort of 135 patients undergoing spinal tumor resection, postoperative complications included weakness in 20% and new sensory deficits in 16.7% of patients.

Infections:

- **Incidence:** Superficial wound infection (aprox. 1.9%)

Details: Among 52 patients treated with a microscopic keyhole approach for spinal intradural extramedullary tumors, 1.9% experienced a superficial wound infection.

Bowel and Bladder Dysfunction:

- **Incidence:** aprox. 3.7%

Details: Urinary and renal complications were observed in 3.7% of patients after spinal cord tumor surgery.

Spinal Deformities:

Details: Extensive surgical procedures, especially those involving significant bone removal, may lead

to postoperative spinal deformities, necessitating further corrective measures.

General Surgical Complications:

Details: As with any major surgical procedure, there are inherent risks of complications such as bleeding, infection, and adverse reactions to anesthesia

Further adverse events are listed in the CRF.

3. Study Sites and Study Population

3.1 Study Site Selection

Due to the rare nature of juxta-medullary tumors and in order to have the opportunity to compare different treatment methods, the trial is planned as a multi-center trial.

So far, 5 centers have expressed interest in participating in the study.

3.2 Study Population

3.2.1 Inclusion Criteria

- Adult, age ≥ 18 years, patients treated on intraspinal, extra medullary tumor
- Patients must have sufficient cognitive and language skills to give informed consent

3.2.2 Exclusion Criteria

- Absence of informed consent
- Lack of ability to consent
- Primary bone tumors
- Vertebral metastasis

3.2.3 Distribution of Gender in the Study Population

All patients treated on juxta-medullary tumors can be invited to participate in the study; distribution of Gender varies depending on histology. For example, spinal meningiomas are up to 80% in female patients (Schwake et al., 2018).

4. Patient Registration

Patients who are cared for at one of the study sites and who are possibly eligible will be invited for study participation. Once written informed consent in participation has been given, the center can register the patient in the electronic data base (Redcap).

Should inclusion criteria fail, or exclusion criteria arise during the following screening process, the patient must be reported to the study coordinator immediately and the patient will be withdrawn from the study.

5. Assessment of Safety

Patients are treated according to the protocol of each center, the participation in the trial does not cause any disadvantage for these patients. Both patients' safety and possible adverse events are

subjects of this study.

6. Statistics

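### The protocol claims that all treated patients are recorded, but the registry holds only invited, consenting patients and nothing counts the rest, so the representativeness of the benchmarks cannot be judged

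*Protocol*

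**What the plan says.** Section 2.3 (Methodology) describes coverage without condition: "All patients treated in one of the study centers are recorded in a databank".

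The entry rules are narrower. Section 3.2.1 requires the skills needed to give consent, and section 3.2.2 excludes on two consent grounds, "Absence of informed consent" and "Lack of ability to consent".

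Invitation is worded in two ways. Section 3.2.3 says "All patients treated on juxta-medullary tumors can be invited to participate in the study", while section 4 says "Patients who are cared for at one of the study sites and who are possibly eligible will be invited for study participation". Section 4 continues: "Once written informed consent in participation has been given, the center can register the patient in the electronic data base (Redcap". No time limit for that database entry is given. The flow chart in section 1.2 places both the eligibility check and consent at admission, in the column before surgery.

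Section 2.2 says what the data are for: to "define benchmarks on quality of life, functionality and neurological outcome" after resection. The synopsis gives benchmarks for extent of resection, functionality and quality of life as the primary objective. Section 6.2 adds a comparison with historical cohorts, from which equivalence or superiority of care is to be described.

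**The concern.** A benchmark is an estimate for a population of operated patients. It can be used only if the reader knows which share of that population it comes from. The coverage sentence in section 2.3 tells the reader that the share is everyone treated, whereas the operative rules yield a subset. Without a count of those outside the subset, neither the sponsor nor a later user of the benchmarks can tell a registry with nearly full capture from one with half.

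The same gap affects the historical comparison in section 6.2, because a difference in patient selection can look like a difference in care. It also affects the comparison of approaches across centres planned in section 2.2: if centres register different fractions, selection is mixed with the differences in practice that are to be studied.

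**Working it through.** The protocol gives no figure on capture, so there is none to reproduce. The check has two parts.

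**1. The rules side by side**

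- *Coverage:* section 2.3 (Methodology) says all treated patients. Section 3.2.2 removes those without consent and those unable to consent. Taken literally, the two do not agree.
- *Invitation:* section 4 uses *will*, section 3.2.3 uses *can*. Neither says that patients are approached consecutively.
- *Registration:* section 4 uses *can*, after consent, with no deadline. Section 1.2 puts consent at admission but has no row for database registration.
- *Counting:* the one reporting duty in section 4 concerns patients found not to meet the criteria in the screening that follows, who are then withdrawn. It does not cover patients who were not invited, who declined, or who were not entered.
- *Checks:* section 7.4 deals with missing or implausible entries. It does not reconcile registered patients with eligible ones. The audit in section 8.1 is optional, and no check of enrolment completeness is named.

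So the protocol text provides no denominator, and the registered fraction cannot be estimated from the data it plans to collect.

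**2. Scale, on assumed inputs**

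Let *c* be the share of eligible patients registered and *d* the difference in outcome rate between registered and unregistered patients. Both are assumptions. Only N = 100 comes from the protocol (section 2.3, Methodology).

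Unseen patients = 100/*c* − 100. Shift in the benchmark = (1 − *c*) × *d*.

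| *c* | Unseen patients | Shift, *d* = 10 points | Shift, *d* = 20 points |
|---|---|---|---|
| 90% | about 11 | 0.1 × 10 = 1 | 0.1 × 20 = 2 |
| 70% | about 43 | 0.3 × 10 = 3 | 0.3 × 20 = 6 |
| 50% | 100 | 0.5 × 10 = 5 | 0.5 × 20 = 10 |

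For comparison, the 95% half-width at n = 100 by the normal approximation:

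- rate 90%: 1.96 × √(0.9 × 0.1/100) = 5.9 points
- rate 80%: 1.96 × √(0.8 × 0.2/100) = 7.8 points

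At 90% capture the shift is small against the sampling error. At 70% it is 3 to 6 points, and at 50% it is 5 to 10 points and can exceed the half-width. Sampling error shrinks as recruitment grows; this shift does not.

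If nothing is assumed about *d*, an observed rate of 90% is compatible with a rate among all eligible patients from *c* × 0.9 to *c* × 0.9 + (1 − *c*). That is 81% to 91% at *c* = 90%, 63% to 93% at 70%, and 45% to 95% at 50%. Knowing *c* would narrow this range at once, and *c* is what the plan does not record.

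**The case against.** The case on the other side is substantial, and much of it stands.

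- *Registration is not shown to be discretionary.* A reader might infer from *can* in section 4 that centres choose whom to enter. The sentence reads equally well as a rule on order: entry is allowed only once consent exists. The preceding sentence also says firmly that possibly eligible patients are to be invited. The point therefore does not rest on centre discretion.
- *Outcome-dependent inclusion is not shown.* A reader might infer that late registration lets the result of surgery decide who enters. The flow chart schedules eligibility and consent at admission, and section 9.2 requires patients to be informed before inclusion. What remains is narrower: a patient who has consented has no stated deadline for database entry.
- *Requiring consent is not a fault.* Patients unable to consent are outside the target population by design and should not be counted as missed eligible patients. No site would take section 2.3 as permission to enter patients without consent, so the sentence does its harm in describing the cohort, not in running the study.
- *The numbers are assumed.* Neither the unregistered share nor the outcome difference is in the protocol. At 90% capture, or with a 10-point difference throughout the range shown, the shift stays below 5.9 points.
- *Other documents are not shown.* The CRF, the user manual and the data validation plan could contain a log.

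None of this supplies a denominator in the protocol text or makes the coverage sentence accurate. Nor can the matter be left to an analysis plan: a count of patients not registered has to be kept at the sites while they are being treated.

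**Conclusion.** The point holds in a limited form. The statement of full coverage in section 2.3 is inaccurate against sections 3.2.1 to 4. The two invitation sentences differ in force, database entry has no deadline, and the protocol text counts no one outside the registry. As a result, the representativeness of the benchmarks for resection, functionality and quality of life, and of the historical comparison, cannot be judged.

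The size is unknown. The range of 1 to 10 points rests entirely on assumed capture of 50% to 90% and assumed differences of 10 to 20 points.

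A reader might go further and conclude that the benchmarks will be too favourable because sicker patients are left out. The document gives no evidence that selection occurs, nor of its direction. A reader might also extend the primary objective to complications and mortality. The synopsis does not include them there; it lists them among the quality indicators under secondary outcomes.

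This is a cheap improvement to what the registry can conclude, not a defect that invalidates it.

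**What to change.** 1. In section 2.3 (Methodology), replace the coverage statement with one that refers to all eligible consenting patients.
2. In sections 3.2.3 and 4, use one rule: every consecutive eligible patient is invited, and each consenting patient is registered before surgery.
3. Have each centre keep an anonymous, count-only screening log: number eligible, invited, consented and registered, and the reason if not registered, with basic tumour type and preoperative McCormick grade where permitted. Because absence of consent is itself an exclusion criterion, define eligible for the log as meeting all criteria apart from having given consent, so that refusals are counted.
4. Report the registered fraction per centre alongside the benchmarks and the historical comparison.

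The cost is a small burden at each site. Treatment and the assessment schedule are unchanged. The log must start with recruitment, since the count cannot be reliably rebuilt afterwards.
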